The efficacy trial design is a mixed method, two level, individually randomised controlled trial of a trauma informed intervention, Trauma Recovery Model Relationship Building Together (RBT), versus business as usual (BAU) for adolescents and young adults served by Bridgend Youth Services (youth justice, edge of care, youth development and early help). There are two levels to the study randomisation. Level one involves selecting staff to be trained in RBT. This allocation is done for all staff, after baseline staff data collection, and is conducted by an on-line independent secure randomisation service, Sealed Envelope Ltd. Consent will be sought from all eligible staff prior to randomisation. As allocations are done at the same time and because we want to maximise balance across the groups on key parameters, we will employ minimisation for the allocation of staff. Our aim will be to maximise balance in terms of service (youth justice, edge of care, children's services, youth development, and early help) and speciality (specialised staff versus generic staff). Provision has been made to conduct a second wave of staff randomisation and TRM training if there is a high turnover of staff throughout the trial – a high turnover is one that exceeds 30%.

Level two allocation involves the randomisation of young people to RBT or BAU. This will be conducted by research staff, using a secure, on-line randomisation service (Sealed Envelope Ltd). after informed consent has been taken and the baseline assessment completed and before any trauma screening has been conducted. The allocation will involve an equal probability of receiving RBT or BAU and will employ random permuted blocks of variable size (4, 6 or 8) with a random block seeded throughout. Randomisation will be stratified by service (youth justice, edge of care, children's services, youth development and early help), sex (male, female), and age group (<15 years, 15 years or more). Stratification variables have been chosen to ensure allocation is balanced across services, sex, and age as some workers specialise in working with older or younger males and females.

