We have used an effect size difference of 0.25 as an important difference; this equates to a difference in volume of offences of circa 12% over a 6-month period, similar effects as found in other psychologically focussed interventions to reduce recidivism in adolescent populations (Hodgkinson et al., 2021). To detect this difference or greater, using a two-sided test, alpha of 0.05 and power at 80% requires 506 young people to be followed-up at our primary endpoint, 6-months post-randomisation, 253 in each group. There is no reliable literature on pre- and post-test correlations for the SRDS, so we have erred on the side of caution and not accounted for this in the sample size calculation as an incorrect assumption increases the risk of an under-powered trial. If we take a potential loss to follow-up of 10%, similar to attrition found in our other studies of young people (Coulton S et al., 2023) this inflates the required baseline sample to 562. We have 73 potential interventionists, 35 randomised to control and 36 randomised to be trained in the intervention delivery. Each interventionist can manage a harmonic mean of 10 young people through the course of the study. To achieve our target, we would need to have at least 56 of these interventionists participating throughout the trial, 28 in each arm, thus allowing for a potential loss of interventionists of 17, 23% of those available.

Assuming only 80% of young people approached consent to take part as found in similar studies (Coulton S et al., 2023) means we would need to approach 702 young people, over the recruitment period. Allowing for a slower start of 20/ per month recruited over the first three months, means 36 will need to be recruited in each month between January 2024 and February 2025, allowing for a six-month follow-up for the interim report submitted in September 2025.

Analysis

All analysis is conducted using STATA 16 SE. Analysis will be conducted and presented in accordance with the CONSORT guidelines. The validity of randomisation will be explored by presenting baseline measures of central tendency and estimates of precision for continuous variables, and proportions for categorical variables broken down by allocated arm and stratification factors for both staff and participant samples.

Primary outcome analysis

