The primary outcome relates to the participant and is the quantity of self-reported delinquent acts in the six months after randomisation assessed using the SRDS. The quantity of delinquent acts is calculated as the sum of positive endorsements for each of the nineteen questions in the SRDS. Two datasets will be created for statistical analysis, the primary analysis will be based on the intention to treat (ITT) dataset. The secondary analyses will examine intervention effects under different scenarios for compliance with allocation (see compliance section below): complier average causal effects (CACE); and per protocol (PP).

The ITT dataset contains all available data for participants who were randomised, regardless of whether they complied with allocation. This dataset will include participants who were withdrawn/withdrew from the trial post-randomisation. These analyses are a lower bound estimate of intervention effects as they represent the effect of offering an intervention, rather than the effect of receiving the intervention.

The primary outcome is the quantity of offences at 6-months post-randomisation. We expect the primary outcome will take the form of a linear distribution. Prior to analysis we will conduct a series of diagnostic tests and assess the underlying assumptions prior to choosing an appropriate and statistically rigorous regression approach. The analysis will take the form of an analysis of covariance using a linear regression. Models will be adjusted by baseline values, quantity of offences in the six months prior to randomisation and stratification factors, service, age group and sex, as covariates. The regression model specification is as follows (eq.1):

$$SRDS6_{i,j} = \alpha + \beta_1(allocation)_{i,j} + \beta_2(SRDS0)_{i,j} + \beta_3(sex)_{i,j} + \beta_4(age)_{i,j} + \beta_5(service)_j + \varepsilon_i$$

Where for participant i within service j ; $SRDS6$ is the 6-month SRDS score, $allocation$ is the allocated group, $SRDS0$ is the baseline SRDS score, sex is the participant sex, age the age group, $service$ the service level dummy variables to adjust for fixed effects and ε_i the individual level error.

An estimate of difference will be generated as a mean difference between the groups and the associated 95% confidence interval.

Secondary outcome analysis

For participants the quantity of offences reported at 12-months will be analysed using similar methods as 6-months (eq. 2).

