We will assess intervention effects in the presence of non-compliance, with compliance measured at the individual level and including all those allocated as part of the trial. Our approach for assessing intervention effects under non-compliance will be via the instrumental variable framework (IV). The benefit of using an IV approach is that randomisation is maintained in the analysis, which is crucial for estimating unbiased intervention effects. In summary, with a binary measure of compliance CACE weights the analysis by treatment allocated (ITT) intervention effect by the proportion of compliers (eq. 5):

$$CACE = ITT / \textit{proportion compliant}$$

If the proportion compliant is 1.0 (i.e. perfect compliance) then the CACE estimate is the same as the ITT estimate, but otherwise the impact of this approach is to increase the magnitude of the intervention effect.

CACE uses a two-stage least squares (2SLS). The first stage model uses intervention received (T) as the outcome, with random allocation (Z) as the independent variable (eq. 6):

$$T = \alpha + Z$$

Based on the stage 1 model, we then calculate predicted values of intervention received (\hat{T}) for use in stage 2. The second stage model predicts the substantive outcome (Y e.g. quantity of offences) using the predicted values of intervention received (\hat{T}) based on the stage 1 model (Eq.7):

$$Y = \alpha + \hat{T} + \varepsilon$$

An additional sensitivity analysis will employ a per protocol approach (PP), containing all data for participants who complete the trial as planned – in intervention and control groups - without any major protocol violations or exclusions. PP analysis essentially drop those individuals who have not strictly complied with their allocation – both those who only partially complied with their allocated intervention and those who did not receive their allocated intervention. This means that PP represents a likely ‘best case scenario’ for intervention effect estimation. The PP dataset will be analysed in a similar manner to the ITT dataset.

Presentation of outcomes

As the sample is large, effect size differences will be calculated using Cohen’s d, specified in the following equation (eq. 8):

$$\delta = (Y_i - Y_o) / S$$

Where Y_i and Y_c are the regression adjusted means, derived from eq. 1, for the intervention and control groups respectively and S is the pooled standard deviation.

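### The two-stage CACE model (SAP eq. 6-7) shows none of the eq. 1 covariates, so as written it rescales an unadjusted ITT difference and is less precise than it need be

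*SAP*

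**What the plan says.** In the SAP, Primary outcome analysis, the ITT estimate comes from a linear ANCOVA (eq. 1): "Models will be adjusted by baseline values, quantity of offences in the six months prior to randomisation and stratification factors, service, age group and sex". The same section introduces the CACE as a secondary analysis.

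Under Compliance, eq. 5 defines the CACE as ITT divided by the proportion compliant, and the text adds: "If the proportion compliant is 1.0 (i.e. perfect compliance) then the CACE estimate is the same as the ITT estimate". The computing rule is two-stage least squares. For eq. 6, "The first stage model uses intervention received (T) as the outcome, with random allocation (Z) as the independent variable", written T = α + Z. Eq. 7 then regresses Y on the predicted T, with an error term and nothing else. The analysis is repeated at five compliance thresholds as a sensitivity analysis. Control participants are said to have no route to RBT.

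The per-protocol set is to be analysed in the same way as the ITT set. No equivalent sentence covers the CACE. The protocol describes the CACE twice (Analysis, and Research Methods of the process evaluation) and names an instrumental-variable framework both times, but no covariates.

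**The concern.** The SAP presents the CACE as the ITT effect rescaled for compliance, so a reader will attribute any difference between the two to compliance alone. If the ITT is adjusted and the CACE is not, they also differ through chance imbalance in baseline SRDS and the stratification factors, and through the wider interval of an unadjusted analysis. Two analysts following this text could report different CACEs, one with covariates and one without. The covariates are already collected, and three of them are stratification factors, so leaving them out gains nothing.

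**Working it through.** **Inputs from the SAP.** Standardised effect 0.25; two-sided alpha 0.05; 80% power; 506 followed up, 253 per arm, 1:1; no control access to RBT.

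**Inputs assumed.** The SAP says there is no reliable pre/post correlation r for the SRDS, so r = 0, 0.3, 0.5 and 0.7 are used. The proportion compliant p is not given; 1.0, 0.8 and 0.6 are used. The simulations use a single normal baseline covariate; the other eq. 1 covariates would act in the same way, through the multiple correlation.

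**Step 1: the plan's own figure.** The normal approximation gives 2 × (1.960 + 0.842)² / 0.25² = 251.2, or 252 per arm. The noncentral t gives 253 per arm (506 in total, power 80.1%). With 10% loss, 506 / 0.9 = 562.2, against 562 in the SAP. The plan's figures are reproduced.

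**Step 2: what eq. 6-7 estimate.** With binary Z and no control access, the stage 1 slope is p, the proportion compliant in the RBT arm. The stage 2 slope is therefore (mean Y in RBT − mean Y in BAU) / p, which is the unadjusted ITT / p. In 3,000 simulated trials per setting the two agreed to about 3 × 10⁻¹⁵. So eq. 6-7 satisfy eq. 5 exactly for the unadjusted ITT.

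**Step 3: distance from the eq. 1 estimate.** At p = 1 the unadjusted and adjusted differences are separated by the fitted baseline slope times the chance baseline difference. In SD units the slope is about r and the baseline difference has SD √(2/253) = 0.0889. The expected absolute gap is therefore about √(2/π) × 0.0889 × r = 0.071 r, that is 0.021, 0.035 and 0.050 for r = 0.3, 0.5 and 0.7. The simulations agree:

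| r | mean absolute gap, p = 1.0 (SD) | mean absolute gap, p = 0.6 (SD) |
|---|---|---|
| 0 | 0.003 | 0.004 |
| 0.3 | 0.021 | 0.036 |
| 0.5 | 0.036 | 0.061 |
| 0.7 | 0.049 | 0.083 |

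The two versions have the same mean, about −0.25 at p = 1.0 and −0.42 at p = 0.6 (true value −0.25 / 0.6 = −0.417). The gap is chance imbalance, not bias.

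**Step 4: precision.** Adjustment multiplies the standard error by √(1 − r²), so omitting the covariate multiplies it by 1/√(1 − r²):

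| r | √(1 − r²) | factor without adjustment |
|---|---|---|
| 0 | 1.00 | 1.00 |
| 0.3 | 0.954 | 1.05 |
| 0.5 | 0.866 | 1.15 |
| 0.7 | 0.714 | 1.40 |

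Simulated ratios of adjusted to unadjusted SD at p = 0.6 were 1.002, 0.952, 0.855 and 0.714, in line with the second column.

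The 95% half-width of the CACE is 1.96 × 0.0889 / p unadjusted, and √(1 − r²) times that when adjusted. At r = 0.5:

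| p | unadjusted (SD) | adjusted (SD) |
|---|---|---|
| 1.0 | 0.174 | 0.151 |
| 0.8 | 0.218 | 0.189 |
| 0.6 | 0.290 | 0.252 |

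**Step 5: does the change restore eq. 5?** With the covariate in both stages, 2SLS equals the adjusted ITT / p exactly at p = 1.0. At p = 0.6 the mean absolute gap is about 0.0006 SD.

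**The case against.** A reader might infer that eq. 6-7 contradict eq. 5 outright. They do not: step 2 shows that they return ITT over the proportion compliant, for the unadjusted ITT. The conflict arises only if ITT in the Compliance section means the eq. 1 estimate. That is the likely reading, because eq. 1 is the only ITT model for the month-6 outcome and the reported effect sizes are built on its adjusted means, but the section does not say so.

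It is also tempting to say that the SAP commits to an unadjusted CACE. Eq. 6-7 are schematic: unlike eq. 1-3 they carry no coefficients or subscripts, and eq. 6 has no error term. The missing covariates could be shorthand. What stands is that the prose also names allocation alone as the regressor in the first stage, and that nothing elsewhere supplies the covariates.

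Bias, or power lost against the plan, might be inferred too. Neither follows. Both versions target the same effect. The 80% planned power already ignores baseline correlation, so an unadjusted analysis only forgoes extra precision (an adjusted ITT test would have about 84%, 90% and 98% power at r = 0.3, 0.5 and 0.7). At r = 0 nothing is lost. Even at r = 0.5 and full compliance the typical gap of 0.036 SD is about a fifth of the 0.174 half-width.

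**Conclusion.** The point holds as one of consistency and precision in a secondary analysis. Read as written, eq. 6-7 give an unadjusted CACE next to an adjusted ITT. At full compliance the two would typically differ by about 0.02 to 0.05 SD for r between 0.3 and 0.7, although the SAP says they coincide (taking ITT as eq. 1). The standard error is larger by a factor of 1.00 to 1.40 over r = 0 to 0.7. These sizes rest on assumed correlations and compliance, a linear model and a normal covariate; the documents cannot narrow them. The primary estimate, its test and the sample size are untouched.

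**What to change.** State under Compliance that the eq. 1 covariates enter both stages:

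- Stage 1: T = a + b1 Z + b2 SRDS0 + b3 sex + b4 age group + b5 service dummies + error
- Stage 2: Y = a + c1 predicted T + the same covariates + error

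Apply this at every compliance threshold and at month 12. Carry across any variable added to the main model under Imbalance at baseline. Say that ITT in eq. 5 is the eq. 1 estimate.

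Fit both stages in one command (in Stata, ivregress 2sls with the covariates as included exogenous variables). The SAP describes computing predicted receipt and then using it in a second regression; the ordinary standard errors of such a manual second stage are not the 2SLS standard errors.

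The cost is a sentence or two in the SAP and one line of code. No new data are needed.

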To explore the role of compliance on outcomes we will conduct a Complier Average Causal Effects analysis (CACE). The definition of compliance with allocation for this trial is as follows (see Table 1 below): (i) those who receive trauma screening (TS) and 80% of RBT interventions offered will be considered 'compliers' in the intervention group (cell A); (ii) those in the control group who did not receive any RBT intervention (cell D). In the intervention group, those attending no trauma screening and/ or less than 80% of interventions offered will be considered 'non-compliers', (cell B). All non-compliers in the intervention group are regarded as being 'contaminated' because they received the control condition (no RBT interventions). For the control group, there is no option for control participants to access the intervention, so there cannot be non-compliance hence this is n/a (cell C).

To further explore the role of compliance on outcomes we will create several thresholds for intervention compliance;

1. TS versus no TS.
2. TS and/ or < 20% of RBT interventions versus TS and >= 20% RBT.
3. TS and/ or < 40% of RBT interventions versus TS and >= 40% RBT.
4. TS and/ or < 60% of RBT interventions versus TS and >= 60% RBT.
5. TS and/ or < 80% of RBT interventions versus TS and >= 80% RBT.

CACE analysis will be undertaken for each threshold and presented as a sensitivity analysis to allow a comparison of outcomes, (RBT group vs BAU) at different thresholds of compliance.

Table 1: Compliance/non-compliance according to group allocation versus intervention received.

	Actually received...	
Allocated to... ↓	Intervention	Control
Intervention	
A. Intervention complier
 
Meeting the stated threshold
	
B. Intervention non-complier
 
Not meeting the stated threshold

Control	
C. Control non-complier
 
n/a
	
D. Control complier
 
Control group participant

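### As defined, the per-protocol analysis can drop low attenders from the RBT arm but not from BAU, so it may be biased in either direction and its best-case label is not assured

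*SAP*

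**What the plan says.** The SAP's Primary outcome analysis makes ITT primary and lists CACE and PP as secondary analyses, pointing to the Compliance section for how compliance is defined. Of ITT it says "These analyses are a lower bound estimate of intervention effects", because ITT estimates the effect of offering the intervention rather than of receiving it.

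In the Compliance section, an RBT participant complies by having trauma screening and 80% of the RBT interventions offered; anyone short of that is a non-complier. For controls the SAP states that "there is no option for control participants to access the intervention, so there cannot be non-compliance", and marks that cell of its compliance table as not applicable.

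The same section adds PP as a further sensitivity analysis. It is to contain participants in both arms who completed the trial as planned without major protocol violations. The SAP explains that "PP analysis essentially drop those individuals who have not strictly complied with their allocation", including those who complied only in part. It calls the result a likely best case "for intervention effect estimation. The PP dataset will be analysed in a similar manner to the ITT dataset". No attendance rule is given for BAU, and major protocol violations are not defined.

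The protocol's Compliance section records the proportion of planned meetings attended in both arms.

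**The concern.** A PP comparison is not protected by randomisation. Here the exclusion rule is also lopsided: the only stated attendance threshold applies to RBT. The retained RBT group is selected on engagement and is compared with a BAU group that is not. The adjustment is that of the ITT model (baseline SRDS, sex, age group and service), and nothing is added for selection.

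The protocol itself does not treat engagement as random. Its Research Methods section plans a latent class analysis to find clusters of non-compliers and groups that are harder to reach. If engagement is related to later offending beyond what the covariates capture, the PP estimate moves away from the true effect.

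The SAP's Presentation of outcomes section reports effect sizes with confidence intervals and p-values and does not exempt PP. A significant PP result beside a null ITT result, under a best-case label and with no warning, could be taken as support for efficacy when it reflects only who attends.

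**Working it through.** **The plan's own figure.** The SAP's Sample size section states "We have used an effect size difference of 0.25 as an important difference" and "To detect this difference or greater, using a two-sided test, alpha of 0.05 and power at 80% requires 506 young people to be followed-up". Allocation is 1:1: "The allocation will involve an equal probability of receiving RBT or BAU". For a two-sided 5% test of 0.25 SD, the normal approximation gives 252 per arm. The noncentral t gives 253 per arm (power 0.801; 0.7998 at 252), which reproduces 506. Allowing 10% loss, 506/0.9 = 562.2, which agrees with 562. The SAP states no figure for PP.

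**Set-up for PP.** Take no true effect and 253 followed up per arm. Let c be the share of RBT participants who meet the threshold, and let ρ be the strength of the correlation between attendance and the 6-month outcome after covariate adjustment, with better attenders offending less. The documents give neither, so both are assumptions shown over a range. Attendance and residual outcome are taken as jointly normal. The lowest 1 − c by attendance leave the RBT arm; no control leaves for attendance.

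**Formulas**, with q the standard normal quantile at 1 − c and λ = φ(q)/c:

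- bias = −ρλ, in residual SD
- retained RBT variance v = 1 − ρ²λ(λ − q)
- SE = √[v/(253c) + 1/253]
- chance of a significant false benefit = Φ(−1.96 − bias/SE)

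**Example, c = 0.6 and ρ = 0.2.** q = −0.253 and λ = 0.644, so bias = −0.129. v = 1 − 0.04 × 0.644 × 0.897 = 0.977. SE = √(0.977/151.8 + 1/253) = 0.102. The chance of a false benefit is 24.3%.

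| c | ρ = 0.1 | ρ = 0.2 | ρ = 0.3 |
|---|---|---|---|
| 0.8 | −0.035; 5.6% | −0.070; 11.2% | −0.105; 20.2% |
| 0.6 | −0.064; 9.1% | −0.129; 24.3% | −0.193; 48.1% |
| 0.5 | −0.080; 11.0% | −0.160; 31.5% | −0.239; 61.1% |

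The nominal chance is 2.5%. At ρ = 0 the bias is zero. If the correlation has the opposite sign, the biases change sign and the false signals point to harm.

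**Simulation check.** 3,000 trials per scenario were analysed by ANCOVA with an assumed baseline–outcome correlation of 0.5. False-benefit rates were 11.0% and 20.4% (c = 0.8), 23.8% and 47.8% (c = 0.6), and 29.2% and 60.5% (c = 0.5) for ρ = 0.2 and 0.3. These are close to the formula.

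**Units.** The biases are in residual SD, whereas the 0.25 target was set without any pre/post correlation and so is in raw SD. With the assumed correlation of 0.5, multiply by √(1 − 0.25) = 0.866: for example, 0.193 × 0.866 = 0.167 raw SD, or 67% of 0.25. The false-benefit rates do not depend on this conversion.

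**Alternatives in the same simulations.** With one attendance rule in both arms and equally selective attendance, the mean PP estimate lay between −0.001 and 0.005 and two-sided error was 4.7–5.7%. ITT was centred on zero with error of 4.7–5.0%. The CACE point estimate was centred on zero to within 0.003.

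**The case against.** Four points on the other side have weight.

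- **The PP definition names both arms.** A reader might infer that nobody can leave the control group. The documents do not say so: a control could be removed for an undefined major violation, and the sentence on control non-compliance concerns access to RBT. What stands is narrower. No stated rule removes a control for low attendance, while one does remove RBT participants.
- **The bias is conditional.** A reader might infer that PP shows benefit whenever there is no effect. It does so only if under-attenders have worse residual outcomes, and the documents give neither the size nor the sign of that relation. Staff carry out the screening, so some non-compliance may reflect delivery rather than prognosis.
- **The ITT wording is defensible.** A reader might take the lower-bound and best-case phrases as a range containing the truth, and want both deleted. The SAP presents no such range. Its lower-bound remark is broadly consistent with its equation 5, under which ITT cannot exceed CACE in magnitude.
- **The hierarchy limits the harm.** ITT is primary, the SAP prefers the instrumental-variable approach because it maintains randomisation, and no decision rule uses the PP p-value. The best-case phrase is hedged and can be read as admitting optimism. It still gives no warning of selection bias, and it is wrong if the bias runs against RBT.

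**Conclusion.** The concern holds in a limited form. The SAP's stated rules allow low attendance to exclude RBT participants from PP and not controls, and the ITT covariates need not remove the resulting selection. The PP estimate can therefore miss the true effect in either direction, and the best-case description is not assured.

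The size depends on two unknowns. Across the assumed range it runs from small (0.035 residual SD and a 5.6% chance of false benefit, at 80% compliance and a correlation of 0.1) to large (0.239 and 61.1%, at 50% and 0.3). These figures also assume joint normality, no true effect and full follow-up of 253 per arm. They show what could happen and do not predict this trial's result. Because PP is only a sensitivity analysis, severity is minor to moderate.

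**What to change.** In the SAP's Compliance section:

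1. Name CACE as the compliance-adjusted estimate. At the 80% threshold it treats partial attenders as having received no RBT, so it has its own limit, but it stays centred on zero if RBT has no effect at any dose.
2. Replace the best-case sentence with a statement that PP is not protected by randomisation and may be biased in either direction.
3. If PP is kept, report it descriptively without a p-value, apply one pre-specified attendance rule to both arms using the meeting records in the protocol's Compliance section, and define major protocol violations. A common rule removes the bias only if attendance is equally selective in both arms.

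The ITT lower-bound wording can stay. The cost is a few sentences in the SAP and no new data collection; the downside is a less prominent version of a customary table.
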